13 CHANGES OR CLARIFICATIONS TO ANALYSES PLANNED IN THE STUDY PROTOCOL

13.1 Changes to the analyses planned in the study protocol

The baseline for PGA-S scores (daytime symptoms) is defined from Visit 3 and not from Visit 1 as stated in the protocol.

Assessments for potential rebound insomnia will be based only on WASO, LPS and sTST for consistency with the primary and secondary endpoints. TST, sWASO and sLSO have been removed.

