3.1.1.3 Safety follow-up phase

The **safety follow-up phase** starts after EODBT. It consists of a single-blind placebo Run-out period of 7 days and a Safety follow-up period.

The **Run-out period** starts in the evening of Visit 9. Visit 9 consists of one PSG night on single-blind placebo treatment. Visit 9 is followed by 6 days at home with single-blind placebo treatment. The eDiary is completed every day during the Run-out period. The end of the Run-out period (End-of-Treatment [EOT]) is reached after all visit assessments have been performed at Visit 10.

The **Safety follow-up period** starts after EOT and ends 30 days after last dose of DB study treatment intake for subjects that are not enrolled in the ID-078A303 extension study.

Subjects who complete DB study treatment and the Run-out period are eligible to enter the ID-078A303 extension study (if approved by the national health authorities and local Independent Ethics Committees / Institutional Review Boards [IECs/IRBs]). For these subjects, the Safety follow-up period ends at the date of enrolment into ID-078A303.

[figure not shown]
End-of-Study (EOS) for an individual subject is defined as the date of the 30-day follow-up telephone call (Visit 11, Day 115) or the date of enrollment into the ID-078A303 extension study. If a subject is prematurely discontinued from study treatment, EOS is performed as planned on Day 115. If a subject withdraws consent and does not wish to

participate in the study any longer, EOS is the date of consent withdrawal for this subject. If a subject is declared lost to follow-up, EOS is the date of last successful contact for this subject.

The visit schedule and protocol-mandated procedures are performed according to the table of assessments [Table 1] and are described in Section 7.

The overall study design is depicted in [Figure 1].

Figure 1 Study design

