6.5 Safety endpoints

In addition to the standardized collection of AEs, safety data specific to insomnia and its treatment will be assessed as follows:

- Withdrawal effects (physical dependence) upon treatment discontinuation will be assessed based on the changes from last assessment on DB treatment (Visit 8, 2nd morning) to run-out period in the BWSQ total score (Visit 9 and Visit 10), the occurrence of relevant AEs and marked ECG abnormalities.
- Rebound insomnia will be assessed based on objective sleep parameters (WASO, LPS and TST) at Visit 9 as compared to Visit 3. It will also be assessed using subjective sleep parameters (sWASO, sLSO and sTST) from run-out period as compared to baseline.
- Next-day residual effect will be assessed based on changes from baseline (Visit 3) to Month 1 and Month 3 in:
 - Coding sub-test[©]
 - SDS[©]
 - Scores on the VAS (mm)
- SAEs up to 30 days after DB study treatment discontinuation or until enrollment into the extension study.
- TEAEs up to 30 days after DB study treatment discontinuation or until enrollment into the extension study.

- AEs leading to premature discontinuation of the DB study treatment.
- AEs of special interest after adjudication by ISB:
 - narcolepsy-like symptoms (i.e., EDS, cataplexy and complex sleep behavior events including hallucinations/sleep paralysis)
 - suicide/self-injury
- Change from baseline (Visit 3) to Month 1 (Visit 6) and Month 3 (Visit 8) in vital signs (mean of the 2 PSG nights in systolic and diastolic blood pressure [BP] and pulse rate).
- Change from baseline (Visit 1) to Month 3 (Visit 8) in body weight.
- Marked ECG abnormalities on DB study treatment.
- Change from baseline (Visit 3) to Month 3 (Visit 8) and the end of the run-out period (Visit 10) in ECG parameters.
- Marked laboratory abnormalities on DB study treatment.
- Change from baseline (Visit 3) to Month 1 (Visit 6) and Month 3 (Visit 8) in laboratory parameters.
- Occurrence of suicidal ideation and/or behavior on DB study treatment based on C-SSRS[®].

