The changes from baseline to the treatment withdrawal period (Visit 9, run-out) in objective sleep parameters (WASO, LPS and TST) will be summarized using descriptive statistics.

The changes from baseline (mean value based on the screening sleep diary entries performed at home in the 7 days immediately preceding the first PSG at Visit 3) to the treatment withdrawal period (after PSG night at Visit 9) in subjective sleep parameters (sWASO, sLSO, and sTST) will be summarized using descriptive statistics.

Next-day residual effect

Observed values and changes from baseline to Month 1 and Month 3 in Coding sub-test[®], SDS[®], and VAS scores (mm) assessing morning sleepiness, daytime alertness and daytime ability to function, will be summarized.

C-SSRS[®]

Number (%) of subjects with suicidal ideation, suicidal behavior, and/or self-injurious behavior without suicidal intent based on the C-SSRS[®] during DB treatment will be tabulated.

Shifts from baseline showing any changes in suicidal ideation and suicidal behavior during DB treatment will also be provided. Subjects will be summarized under the worst of the following three categories, shown here in the order from best to worst: 1) No suicidal ideation or behavior, 2) Suicidal ideation only, and 3) Suicidal ideation and behavior.

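### The SAP drops sWASO and sLSO from the rebound-insomnia analysis, so sleep onset and sleep maintenance after withdrawal are summarized from one PSG night only

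*SAP*

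**What the plan says.** Protocol 6.5 sets out the rebound endpoints in two parts. The objective part reads "Rebound insomnia will be assessed based on objective sleep parameters (WASO, LPS and TST) at Visit 9 as compared to Visit 3". The subjective part reads "It will also be assessed using subjective sleep parameters (sWASO, sLSO and sTST) from run-out period as compared to baseline". Section 10.3.3 repeats the plan for the Treatment Withdrawal Set: changes from baseline "in subjective sleep parameters (sWASO, sLSO, and sTST) will be summarized using descriptive statistics".

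On data collection, Protocol 3.1.1.3 says "Visit 9 consists of one PSG night on single-blind placebo treatment" and "The eDiary is completed every day during the Run-out period". Protocol 3.2.1 gives the diary a purpose of its own: with the one PSG night, the entries from the three days after stopping treatment are meant to show rebound.

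SAP 13.1 changes this: "Assessments for potential rebound insomnia will be based only on WASO, LPS and sTST for consistency with the primary and secondary endpoints". It then adds "TST, sWASO and sLSO have been removed". SAP 7.7 follows suit, summarizing WASO and LPS at Visit 9 and sTST from the run-out diary. SAP 4.2 lists the same three variables.

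**The concern.** Safety and tolerability on stopping treatment is a stated objective (Protocol 2.3), and the sponsor intends a claim in sleep onset, sleep maintenance or both (Protocol 10.3.1.1). Rebound in those two properties is therefore what a reader of the withdrawal results will look for.

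The reason given for the change concerns alignment with efficacy endpoints. It does not say whether the reduced set can still detect rebound. There is also an asymmetry. SAP 6.2 keeps sWASO and sLSO as efficacy variables on treatment, with model estimates, confidence intervals and p-values. The same diary items are not summarized for worsening after withdrawal.

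At stake is a rebound in falling or staying asleep that appears after the Visit 9 night without shortening total sleep enough to show in sTST.

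**Working it through.** The plan states no figure on this point. The check traces each variable from endpoint to data to analysis, and counts the nights behind each measure.

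**1. Measures by aspect of sleep**

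| Aspect | Protocol: Visit 9 PSG night | Protocol: run-out diary | SAP: Visit 9 PSG night | SAP: run-out diary |
|---|---|---|---|---|
| Onset | LPS | sLSO | LPS | none |
| Maintenance | WASO | sWASO | WASO | none |
| Total sleep | TST | sTST | none | sTST |

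Multi-night measures go from 3 to 1, and none is left for onset or maintenance.

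**2. Does another SAP section fill the gap?** No.
- SAP 6.2 summarizes sWASO and sLSO at Month 1, at Month 3 and by week. Table 7 ends at Study day 85 and excludes run-out values.
- SAP 6.3 takes self-reported awakenings, the sleep-quality VAS and the night-time PGI items to Month 1 and Month 3 only. The PGI items are also collected at Visit 10 (Protocol 7.2.2.6 and 7.2.2.7).
- Run-out diary values may appear in listings, but no summary of sWASO or sLSO is planned.

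**3. Nights available.** The SAP 12.8 run-out window runs from the day after the Visit 9 PSG morning to the earlier of seven days after that morning and Visit 10. Visit 9 falls on Day 85/86 and Visit 10 on Day 92 (+2 days).
- PSG morning Day 86, Visit 10 on Day 92: Days 87 to 92 = 6 days.
- PSG morning Day 86, Visit 10 on Day 93 or 94: Days 87 to 93 = 7 days.
- PSG morning Day 85: Days 86 to 92 = 7 days.

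Onset and maintenance could each rest on 6 to 7 diary days besides the single PSG night.

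**4. Why sTST does not stand in.** sTST is one reported total (SAP 6.1.2). As an approximation, sTST ≈ time in bed − sLSO − sWASO, so change in sTST ≈ change in time in bed − change in sLSO − change in sWASO. The documents give no run-out data on time in bed, so the following is an assumed range. Take sLSO worse by 30 min and sWASO unchanged:
- time in bed unchanged: 0 − 30 = −30 min, visible in sTST;
- time in bed 15 min longer: 15 − 30 = −15 min;
- time in bed 30 min longer: 30 − 30 = 0 min, invisible in sTST.

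Even in the first case sTST cannot tell an onset problem from a maintenance problem.

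**5. Why TST is not part of the gap.** PSG recording is fixed at 480 min (Protocol 7.2.2.1). LPS runs from the start of recording to persistent sleep, and WASO covers waking from there to lights on. Hence TST = 480 − LPS − WASO + any brief sleep before persistent sleep. Visit 9 TST was always a one-night value, and it is largely determined by two variables that are kept.

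**6. Dilution in a weekly mean.** A worsening of d minutes on k of 6 diary nights moves the mean by k × d / 6. With d = 30 (illustrative): k = 1 gives 5 min and k = 3 gives 15 min. A weekly mean alone would blunt the short rebound that Protocol 3.2.1 has in view.

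**The case against.** The change is declared in SAP 13.1 with a reason. Sleep onset and maintenance are still measured objectively on the first night off drug. The Treatment Withdrawal Set still has sTST over the run-out window, with distribution plots and threshold tables that Protocol 10.3.3 did not list, and adverse events starting or worsening during withdrawal are tabulated. Without full compensation by longer time in bed, worse latency or more waking would tend to lower sTST. All of this stands, and it makes the loss partial.

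Five stronger readings are tempting and should not be drawn:
- *Three of six rebound variables are lost.* The count is right, but TST is nearly redundant once LPS and WASO are kept. The substantive loss is two diary variables.
- *The diary is the only multi-night source.* The night-time PGI items at Visit 10 look back over seven nights and mention trouble falling asleep and waking. They do not close the gap, because the SAP does not analyse them at that visit.
- *Home time in bed in run-out is 6 to 9 h.* Protocol 7.2.2.2.1 gives that range as a run-in eligibility expectation for at least half the nights between Visits 2 and 3. Full offset in sTST is possible; nothing shows that it is likely.
- *Later rebound would go unreported.* One that shortens total sleep or is reported as an adverse event would still be visible.
- *This is an undisclosed deviation.* It is disclosed.

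None of this answers the narrow point: the stated reason does not bear on safety after withdrawal, and no multi-night summary of onset or maintenance remains.

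**Conclusion.** The point holds for sWASO and sLSO. Under the SAP, sleep onset and sleep maintenance after withdrawal are each summarized from one PSG night, where the protocol also planned a multi-night diary measure of each. What may be missed is an onset or maintenance rebound after the Visit 9 night that neither lowers average sTST visibly nor is reported as an adverse event. How often that would happen cannot be judged from the documents.

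The day counts in the working assume visits on the scheduled days and complete diaries. The time-in-bed and dilution figures are illustrations. The analyses are descriptive and outside the alpha-controlled testing, so efficacy conclusions, type I error and power do not change. This is a cheap improvement, not a flaw that threatens the trial's main result.

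**What to change.** 1. In SAP 7.7, restore sWASO and sLSO as descriptive changes from baseline on the Treatment Withdrawal Set, using the run-out window already in 12.8. Baseline, diary items and the two-day minimum for a mean are already defined for both variables (SAP 6.2, 10.1, 12.8).
2. Add a by-night summary of the first diary nights, to match the three-day purpose in Protocol 3.2.1. State whether the diary entry for the Visit 9 night counts among them, since the 12.8 window starts after it.
3. Amend SAP 4.2 and 13.1 to agree.
4. Restoring Visit 9 TST is optional. It would match the protocol but add little information.

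The cost is a few more descriptive tables from data already collected, with no new assessments.

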13.2 Changes in the conduct of the study / data collection

Not applicable.

13.3 Clarifications concerning endpoint definitions and related variables or statistical methods

The VAS scores related to depth of sleep, daytime alertness and ability to function will be analyzed as efficacy variables [Section 6.3] and not as safety variables. The VAS score remaining as a safety variable is the question from the sleep diary related to morning sleepiness [Section 7.8].

TEAEs that started or worsened during the safety follow-up period will only be listed. Summary tables for TEAEs, TEAEs related to study treatment, TEAEs related to abuse and TEAEs based on selected Standardised MedDRA Queries or pre-defined search criteria will include only those TEAEs occurring during the DB study period.

The handling of the missing data for the weekly calculation of the subjective endpoints, which includes the secondary endpoints, will be aligned: subjects must have at least 2 days of data during each week to calculate a weekly mean [Section 10.1].

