2.3 Safety objectives

To assess the safety and tolerability of ACT-541468 in subjects with insomnia disorder during treatment and upon treatment discontinuation.

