One PSG night is planned after the first day of treatment discontinuation and the sleep diary completed in the 3 days following treatment discontinuation will allow assessment of rebound insomnia on objective and subjective parameters, respectively. Thus, this 7-day run-out period allows to capture long-term withdrawal effects, as well as shorter-term potential rebound symptoms.

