5.1.9 Premature discontinuation of study treatment

The decision to prematurely discontinue study treatment may be made by the subject, the investigator, or Idorsia personnel. The main reason for discontinuation must be documented in the eCRF and in the subject's medical charts (e.g., AE, lack of efficacy).

A subject has the right to prematurely discontinue study treatment at any time, without any justification, by withdrawal from study treatment only or by withdrawal from any further participation in the study (i.e., premature withdrawal from the study [see Section 8.2]). Although a subject is not obliged to give his/her reason for prematurely withdrawing from the treatment or the study, it is recommended that the investigator makes a reasonable effort to ascertain the reason(s), while fully respecting the subject's rights.

The investigator must discontinue study treatment for a given subject if, on balance, he/she believes that continued administration would be contrary to the best interests of the subject.

Study-specific criteria for discontinuation of study treatment are described in Section 5.1.10.

A subject who prematurely discontinues study treatment is NOT considered as withdrawn from the study and will be followed up until the planned EOS (Day 115), provided that the subject's consent for this limited participation in the study has not been withdrawn. The subject is recommended to return for safety assessments [see Table 1] within one week of his/her last DB study treatment intake (N.B., next day residual assessments will only be performed if the subjects can be assessed within 24 h of last DB study drug intake). All subjects withdrawn from study treatment are encouraged to follow planned study procedures (e.g., visits, sleep diary and questionnaire completion) until EOS. In this case, the run-out period (including Visit 9 and Visit 10) will not be performed, and subjects will directly enter the follow-up period after Visit 8 (considered as EOT in the event of premature discontinuation). The phone call will be performed as planned 30 days (+ 7 days) later, at Visit 11. This will decrease the amount of missing data which is important from a study integrity perspective. Subjects who prematurely discontinue study treatment or the study for any reason will not be replaced.

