5.4.2 Study treatment compliance

Study treatment compliance will be assessed through study treatment accountability.

Study treatment compliance per wallet dispensed is entered in the electronic case report form (eCRF) for the Run-in period, the DB study period, and the Run-out period and will only be listed.

The following formula will be used to calculate compliance for each of these periods:

Study treatment compliance (%) = $[(\text{number of tablets dispensed} - \text{number of tablets returned}^*) / (\text{treatment duration} - \text{total duration of treatment interruptions})] \times 100$

* If a subject did not return his wallet (e.g., it is lost), compliance will not be calculated and the compliance for the period will be set to missing.

Treatment duration and total duration of treatment interruptions in Run-in, DB, or Run-out periods are calculated using the dedicated eCRF page ‘Study Treatment Log’ as follows:

- Treatment duration (days) = date of last drug intake of DB study treatment (run-in / run-out single-blind placebo treatment) – date of first drug intake of DB study treatment (run-in / run-out single-blind placebo treatment) + 1 day.
- Total duration of treatment interruptions (days) is the sum of all the treatment interruptions’ durations. A treatment interruption duration = date restarted DB study treatment (run-in / run-out single-blind placebo treatment) – end date of DB study treatment (run-in / run-out single-blind placebo treatment) due to an interruption – 1 day. For example, if a subject stopped his/her treatment on 19MAR2019 and started again on 23MAR2019, as the treatment is taken on the start and end dates, the calculation will be 23MAR2019–19MAR2019 – 1 day = 3 days of interruption. Should the subject interrupt the treatment again for 7 days, the total duration of interruptions will be 10 days. For subjects who complete the study treatment for a given study period but end on an interruption before continuing study treatment in the next study period,

the start date of the next study period will be used as the date restarted study treatment of the given study period. E.g., if a subject completed DB study treatment with an interruption on 23JUN2019 and then started the treatment withdrawal period on 26JUN2019, the duration of that treatment interruption will be $(26\text{JUN}2019 - 23\text{JUN}2019) - 1 \text{ day} = 2 \text{ days}$.

The percentage of days treated is defined as follows:

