7.2 Adverse events

Unless noted otherwise, the AE summary tables will include treatment-emergent AEs (TEAEs): AEs that started or worsened on or after DB study treatment start date up to the earlier of 30 days after DB study treatment end date or the date of enrollment into the ID-078A303 extension study. An AE that started or worsened during any planned or unplanned study treatment interruption (e.g., run-out, safety follow-up) that is falling in the treatment-emergent time window defined above, will be considered as treatment-emergent.

AEs will be coded using MedDRA. The MedDRA version used for reporting will be specified in the footnote of the applicable output.

The number (%) of subjects experiencing a TEAE (including serious AEs [SAEs], AEs of special interest [AESIs] after adjudication by the Independent Safety Board [ISB], and AEs leading to premature discontinuation or temporary interruption of DB study treatment) will be summarized by SOC and/or PT, and/or maximum intensity.

Each AESI category (i.e., excessive daytime sleepiness, cataplexy, complex sleep behavior including hallucinations / sleep paralysis, suicide/self-injury, narcolepsy-like symptoms) will be summarized by PT separately.

A subject with multiple intensities reported for an AE will be summarized under the maximum intensity recorded for the event.

Apart from the summaries of occurrences, where each event is counted, a subject with multiple occurrences of an AE is counted only once in the AE category (e.g., SOC, PT). If a single AE worsens on the same treatment group, then this event will be considered as one occurrence. AEs will be sorted by descending frequency, first in the highest ACT-541468 dose level, then in the next highest ACT-541468 dose level, and finally in the placebo treatment group. After this sorting, SOCs are presented in alphabetical order with PT sorted within SOC in alphabetical order.

The following AE summary tables will be provided:

- Treatment-emergent AEs.
- Treatment-emergent AEs during the DB study period^a.

- AEs occurring (i.e., that started or worsened) during the Run-in period.
- AEs occurring (i.e., that started or worsened) during the treatment withdrawal period (based on the TWS).
- TEAEs during the DB study period^a related to study treatment.
- AEs leading to premature discontinuation of DB study treatment.
- AEs leading to temporary interruption of DB study treatment.
- Treatment-emergent SAEs (including occurrences).

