12.2 Study periods

The Screening period is defined as the time from the informed consent date until one day before the Run-in period start date.

The Run-in period is defined as the time from the start of the run-in single-blind placebo treatment to one day before start of DB study treatment or, for those not starting DB study treatment, to run-in single-blind placebo treatment end date.

The DB study period is defined as the time from the day of DB study treatment start until the day of EODBT (Visit 8, 2nd morning), or, for those who prematurely discontinued DB study treatment (i.e., those without an EODBT date), until one day after DB study treatment end date (if the treatment is taken before midnight) or the day of DB study treatment end date (if the treatment is taken after midnight). Time of treatment intake between 00:00 and 11:59 is considered as 'after midnight', while a time between 12:00 and 23:59 is considered as 'before midnight'. For any missing or incomplete time, it is presumed that the treatment was taken before midnight. For subjects who complete DB study treatment with an

interruption before continuing the run-out single-blind placebo treatment, the end of DB study period is the run-out single-blind placebo treatment start date – 1 day.

For those subjects in the TWS, the treatment withdrawal period (or Run-out period) is defined as the time from one day after the end of the DB study period to the latter of seven days after the end of the DB study period or Visit 10 date.

The safety follow-up period is defined as the time from one day after the end of the treatment withdrawal period for those starting the treatment withdrawal period (i.e., subjects in the TWS) until EOS date; or from one day after the end of the DB study period for those not starting the treatment withdrawal period until EOS date.

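### SAP 13.3 contradicts the 30-day adverse event tables of SAP 7.2, an interruption at the end of treatment delays the withdrawal clock, and early stoppers' first week off drug enters no withdrawal table

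*SAP*

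**What the plan says.** **Reporting of late events.** SAP 13.3 states that "TEAEs that started or worsened during the safety follow-up period will only be listed". Its next sentence confines four kinds of summary table to the DB period: TEAEs in general, treatment-related TEAEs, abuse-related TEAEs, and those from standardised or pre-defined searches. SAP 7.2 defines a TEAE by a window that closes 30 days after DB treatment ends, or at enrolment into the extension if earlier. It then lists tables of all TEAEs, serious events, adjudicated events of special interest and fatal events on that window. A separate table covers events "during the treatment withdrawal period (based on the TWS", the Treatment Withdrawal Set).

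**Who is in that set.** Protocol 10.1.5 and SAP 4.1.5 both require run-out placebo to have been received. For subjects who stop early, Protocol 5.1.9 says "the run-out period (including Visit 9 and Visit 10) will not be performed". SAP 12.2 places their off-drug days in safety follow-up: "or from one day after the end of the DB study period for those not starting the treatment withdrawal period until EOS date".

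**Where the DB period ends.** Under SAP 12.2 it ends on the second morning of Visit 8 for an ordinary completer, and one day after the last evening dose for an early stopper. For a completer who has an "interruption before continuing the run-out single-blind placebo treatment, the end of DB study period is the run-out single-blind placebo treatment start date" minus one day. SAP 5.4.2 illustrates such a subject, who "completed DB study treatment with an interruption on 23JUN2019 and then started the treatment withdrawal period on 26JUN2019".

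**Purpose.** Protocol 2.3 covers safety "during treatment and upon treatment discontinuation". For rebound, Protocol 3.2.1 says "One PSG night is planned after the first day of treatment discontinuation".

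**The concern.** The off-drug week answers part of the safety objective, so each event in it needs one unambiguous home and a clock that starts at the last active dose. In three places this fails.

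- A programmer cannot satisfy both SAP 7.2 and SAP 13.3, so whether a post-treatment event is counted in a table or only listed is left open.
- For a completer who ends on an interruption, some off-drug days are labelled double-blind. An event on those days is reported as arising in the DB period, and the only rebound polysomnography (PSG) night comes later than the protocol intends.
- A subject who stops early has adverse events collected to End-of-Study, yet the days just after stopping reach no withdrawal display.

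**Working it through.** **1. The SAP's own gap figure.** SAP 5.4.2 computes an interruption as restart date minus last intake date minus 1. Its June example gives 26 - 23 - 1 = 2 days, and its March example gives 23 - 19 - 1 = 3 days. Both reproduce. In the June case the undosed nights are 24 and 25 June.

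**2. SAP 12.2 applied to each type of subject.** Let L be the date of the last DB dose, taken before midnight.

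| Subject | DB period ends | Next period starts | Label of that period |
|---|---|---|---|
| Ordinary completer | L+1 (Visit 8, second morning) | L+2 | withdrawal |
| Early stopper | L+1 | L+2 | safety follow-up |
| Completer with terminal gap of k days (k ≥ 1) | L+k (run-out start minus 1) | L+k+1 | withdrawal |

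The first two rows share one clock and differ only in label. The third row departs from it by (k+1) - 2 = k-1 days.

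**3. The June example (k = 2).** Under the stated rule the DB period ends on 25 June and withdrawal runs from 26 June (L+3) to at least 2 July. Under the early-stopper rule the DB period would end on 24 June, and seven days of withdrawal would run from 25 June (L+2) to 1 July. One off-drug day, 25 June, is therefore counted as double-blind.

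**4. The rebound night.** Run-out begins on the evening of Visit 9 (Protocol 3.1.1.3), so the Visit 9 PSG falls on off-drug night k+1.

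| Gap k (days) | Withdrawal days counted as DB (k-1) | Off-drug night of Visit 9 PSG (k+1) |
|---|---|---|
| 1 | 0 | 2 |
| 2 (SAP example) | 1 | 3 |
| 3 | 2 | 4 |
| 7 | 6 | 8 |

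With no gap the PSG is on night 1, as intended.

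**5. One event traced through the text.** Take an early stopper with an adverse event at L+3, not enrolled in the extension.
- SAP 12.2: the event is in safety follow-up.
- SAP 13.3: it is listed only.
- SAP 7.2: it is within 30 days, so it belongs in the overall TEAE table, and in the serious, special-interest or fatal table if it qualifies.
- Withdrawal table: excluded, because the subject has had no run-out dose.
- SAP 7.1: an ECG, laboratory or vital-sign value from that same day would count as taken during DB treatment.

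**6. How many early stoppers.** SAP 6.1.4 reports 14 of 356 stopping early in a one-month Phase 2 study: 14/356 = 3.93%.
- The same total over this trial: 0.0393 × 300 = 11.8, about 12 per arm (24 of the 600 on active drug).
- Assuming a constant monthly rate for three months: 1 - (1 - 0.0393)³ = 11.3%, and 0.113 × 300 = 34 per arm (68 of 600).

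The documents give no rate for ending on an interruption.

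**The case against.** **The withdrawal set is deliberate.** The protocol itself assigns withdrawal and rebound to subjects who received run-out placebo. Run-out is a concealed switch with fixed Visit 9 and Visit 10 assessments; early stoppers know that they stopped, have shorter and varying exposure, and have no such visits. This stands. It is why a separate descriptive table is proposed and not a change of analysis set. It also means that the SAP 13.3 sentence is not what keeps early stoppers out: deleting it would put none of them into a withdrawal table.

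**Their data are not lost.** On SAP 7.2 their events reach the 30-day tables, and all safety data are listed. The SAP history records the TEAE summary as restored to 7.2, which suggests that 13.3 is leftover text. That makes the likely intention clear, but the current sections still conflict, and the overall table mixes on-drug and off-drug events.

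**Terminal gaps are short and rare.** Protocol 5.1.8 asks for interruptions to be kept as short as possible, and doses on PSG nights are given at site. A one-day gap does not shift the adverse event window at all. This stands as to size. However, Protocol 5.1.8 sets no maximum, and the SAP has written specific rules for the case.

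**The 11% is weak.** Four of the 14 Phase 2 stoppers were randomized in error or did not meet criteria, two withdrew consent, and the SAP expects only a slightly higher rate. Subjects who withdraw consent contribute no later data, so not every early stopper could appear in a new table. The figure of 34 per arm is an illustration at the upper end.

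**What a reader might wrongly infer.** One might conclude that the whole withdrawal window is tied to run-out and not to the last dose. It is not: ordinary completers start at L+2 either way. One might also conclude that the plan steers the results towards no effect, or that some subjects have passed the withdrawal window before it opens. The visible text gives no half-life for this drug, only that seven days exceed five half-lives, and nothing shows that early stoppers, with shorter exposure, have more or fewer withdrawal effects.

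**Conclusion.** The point holds in three limited parts.

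1. SAP 13.3 and SAP 7.2 contradict each other on events after the DB period. This rests on the text alone.
2. For completers who end on an interruption, SAP 12.2 counts k-1 off-drug days as double-blind and the rebound PSG falls on night k+1. In the SAP's own example that is one day and night 3, assuming an evening last dose. The number of such subjects is not given and is probably small.
3. Early stoppers' first off-drug week enters no withdrawal table, by the protocol's design, although adverse events are collected and the objective covers stopping. About 12 per arm are affected if 3.9% stop in total, and about 34 if that monthly rate held for three months.

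The timing is right for ordinary completers, and the effect of leaving out early stoppers could go either way. No primary or secondary efficacy analysis is touched. The changes are still worth making: the first two parts are faults in stated rules, and the third can be met descriptively.

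**What to change.** (a) **SAP 13.3:** delete the first sentence, and from the second delete only the general TEAE entry, so that the section agrees with 7.2. Keep the treatment-related, abuse-related and search-based tables as DB-period tables, as 7.2 already has them.

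(b) **SAP 12.2:** for adverse event assignment, end the DB period of completers who finish on an interruption one day after the last DB intake (on the day of intake if it was after midnight), as for early stoppers. Start the withdrawal period on the next day.

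(c) **SAP 7.6 and 7.7:** alongside the full Treatment Withdrawal Set, show the Visit 9 PSG rebound summary and the Visit 9 change in the Benzodiazepine Withdrawal Symptom Questionnaire restricted to subjects whose last DB dose was on the evening before the first run-out dose.

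(d) **SAP 7.2:** add one descriptive adverse event table on the Safety Set, by arm, separately for Treatment Withdrawal Set subjects and early stoppers. Count onsets from the day after the corrected DB period ends (L+2 after an evening dose) for seven days, or to Visit 10 if later. Starting at L+1 would count an event on the last DB day in two tables. Add a footnote that early stoppers knew they had stopped and had shorter exposure.

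The questionnaire taken at an early Visit 8 should not be added to the withdrawal endpoint, which is defined as a change to Visits 9 and 10.

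**Cost:** SAP wording and one or two tables from data already collected, with no change to visits, procedures or randomization. The early-stopper group will be small and its rows will be imprecise.
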